1.3 Rationale

Evidence from the community indicates that social care improves individuals' health, quality of life, and well-being (34). Despite a lack of robust studies, this appears to generalise into prisons, where social care programmes have a positive impact on prisoners including where there are unmet needs linked to health complications (21,35,36). Strong social care delivery can also ease compound pressures on the NHS (37) and reduce rates of recidivism (38,39). Our proposed study aligns with key NIHR, Department of Health and Social Care (DHSC), His Majesty's Prison and Probation Service (HMPPS), and government priorities, including improving the lives of people with long-term conditions and the underserved prison community (40), reducing reoffending (41), and improving integrated social care (45). As older adults are the fastest growing population in prisons (42), social care is becoming a growing concern (17). Evidence from this study could revolutionise social care in prison system within the next 10 years.

To our knowledge, there have been no previous RCTs of a social care intervention in prison. This study is therefore uniquely placed to evidence what effective social care in prison looks like and how it can be successfully integrated with healthcare. The first part (WP1) will result in an optimal package of tools both for implementing the package and assessing it, followed by a feasibility RCT and embedded formative process evaluation (WP2).

1.4 The Intervention

As part of a Programme Development Grant (202610), we used the findings of a realist review to develop an IPT and logic model of co-ordinated social care in men's prisons (33). The realist synthesis allowed us to explore what works for whom and in what circumstances (43) through examination of the community and prison-based literature, and stakeholder engagement workshops. Our expert by experience group named the intervention 'Empowered Together' (ET). ET has potential to lead to direct service user benefit by providing systematic assessment and coordination of social care. The ET intervention follows the three principles of being:

- Trauma Informed
- Integrated
- Person-centred

Trauma informed care: Individuals in prison have often experienced significant trauma in their lives and through the process of imprisonment (44). Trauma-informed practice is an approach to interventions that is grounded in an understanding that exposure to trauma can impact a person's biological, neurological, psychological and social development (45). It acknowledges the need to see beyond an individual's presenting behaviours and ask, 'What does this person need?' rather than, 'What is wrong with this person?'. Its key principles include choice; collaboration; cultural considerations; empowerment; safety; and trustworthiness (46).

Integrated care: It has been evidence that that the way in which prison health and social care is delivered is impeded by silo working (47). Integrated care joins up the health and care services required by individuals to deliver care that meets their personal needs in an efficient way. For individuals with social care needs in prison, this will include coordinating care with criminal justice, health, social care, third sector, families, peers, and the individual themselves.

Person-centred care: Individuals living in prison often feel extremely limited in their choices regarding their health and social care (48). Being person-centred is about focusing care on the needs of the individual, ensuring that people's preferences, needs and values guide clinical decisions, and providing care that is respectful of and responsive to them (49).

1.5 Assessment and Management of Risks relating to this study

The risk of harm in this study is small, as activities will take place with assenting and consenting participants who have the capacity to understand the situation, and in a regulated environment (a prison, with prison staff aware of the research activities). Nevertheless, we acknowledge that participants may have mental disorders or other vulnerabilities and so might become distressed during research activities, and that their reasons for being in prison may include a propensity for violence. We have considered how to respond in the unlikely event of serious distress or threats.

Risks to Participants

There is a possibility that participants might experience discomfort or distress during workshops, feasibility RCT activities, or interviews. Participant Information Sheets (PIS) that describe ethical rights as well as the relevant research activities will be given to participants to help prepare them and minimise burdens and risks as far as possible. All activities will be carried out by experienced, trained researchers and staff, in conjunction with robustly trained experts by experience where possible. Researchers and staff will be aware of the sensitivities surrounding the activities and will carefully choose their approach to prioritise the comfort and ease of participants.

If a participant becomes distressed, researchers will draw on the approach outlined in Jefferson and Holloway (50), who advise that their role is one of emotional containment. For the workshops and interviews, this will involve offering participants the option to take a short break, and being guided by them as to whether to continue with the session. Researchers will have training to aid them in this decision. If a participant becomes significantly upset, researchers will adhere to the study safeguarding protocol. The consent process will make it clear that if a participant tells the researcher that they intend to harm themselves or someone else, confidentiality will be broken and relevant services will be informed immediately. Researchers who conduct interviews with people in prisons are also obligated to report the following and will make this clear to prospective participants in the PIS:

- Behaviour that is against prison rules
- Information that either indicates a risk or harm to the participant or others
- Information on previously undisclosed illegal acts or plans to commit a new crime
- Information that raises concerns about terrorist, radicalisations, or security issues
- Information about poor or unacceptable practices by the prison staff or by an outside organisation

Risks to Staff (ET Workers and Researchers)

Although risks of harm to researchers are small, we will take every step to ensure that prison staff are fully aware of our whereabouts at all times while we are in the prison and we will complete University of Manchester (UOM) training on identifying and managing risks, as well as prison induction training, which covers corruption prevention, health and safety, security measures, and safer custody procedures. Whilst interacting with prisoners, researchers will be based in an environment where there is an alarm and where prison staff will be on duty nearby at any given time. In advance of meeting the researcher, the potential participant will have been screened by the prison contact for level of risk to the researcher.

Psychological risks are low but include discomfort or distress from working with a traumatised population in challenging environment. To mitigate this, clinicians within the research team will be available to guide and support staff throughout the project. Regular meetings between the fieldworkers and senior researchers will include discussion of data collection processes to provide a safeguarding framework and identify changes to procedures if needed.

2. OBJECTIVES AND OUTCOME MEASURES

The aims of WP1 (development work) and WP2 (feasibility RCT and embedded formative process evaluation) are to address the following research questions:

- 1. Can we implement the ET intervention in two men's prisons?
- 2. Is it acceptable and feasible to conduct an RCT to assess whether ET improves the number of met social care needs for adults in prison who are likely to have unmet needs after six weeks and three months, in comparison with care as usual?

2.1 Objectives

Primary Objectives

WP1: to develop communication, training, and trial materials, including a training and supervision manual, fidelity of implementation tool, and audio, blog, event, film, and webpage content.

WP2: to determine the acceptability and feasibility of a full RCT, including through:

- Conducting a feasibility RCT. We will implement ET in two prisons and then assess rates of recruitment and outcome measure completion; intervention adherence and fidelity; and rates of retention and transfer or release during follow-up.
- Conducting cost-effectiveness feasibility evaluation. We will estimate resource use and delivery costs for ET, and develop and test methods for undertaking a cost-effectiveness analysis alongside a full trial.

- Conducting a realist-informed formative process evaluation. We will explore barriers to the acceptability and feasibility of intervention and trial design (and develop methods to overcome these where possible); evaluate risk of bias or contamination; evaluate fidelity of intervention delivery; and explore mechanisms of action of ET (i.e., what works, in what circumstances, for whom, and how).
- Reviewing findings against progression criteria and if met developing a final RCT protocol. If not met, alternative methods of evaluation will be reviewed.

Secondary Objectives

WP2: to collect patient outcomes data to inform a full RCT, including assessing the acceptability of the measures used.

2.2 Outcome Measures

Primary Outcomes

WP1:

- A training and supervision manual (nine months after project commencement)
- A fidelity of implementation tool; this will be completed by a researcher in WP2 at the end
 of the three-month intervention to assess whether the intervention has been delivered in
 accordance with the protocol and manual, and to evaluate the quality of delivery
- Audio, blog, event, film, webpage content (18 months after project commencement)

WP2:

For the feasibility RCT, the below traffic light criteria will be used in the decision-making process. However, outcomes will be reviewed as a whole, such that amber or red ratings on one or more of the objectives will not necessarily prevent progression to a full trial:

- Delivery of ET at each site (at end of feasibility RCT)
 - o Green: both sites able to deliver ET
 - o Amber: one site able to deliver ET
 - o Red: no sites able to deliver ET
- Number screened, eligible, and recruited into trial (once marked eligible from screening)
 - o Green: 60% of participants recruited
 - Amber: 40-60% of participants recruited
 - o Red: <40% of participants recruited
- Outcome measure completion rates (at 42- and 90-days ±7 days post-randomisation)
 - o Green: 80% of participants have completeness of >60%
 - o Amber: 60-80% of participants have completeness of >60%
 - o Red: <60% of participants have completeness of >60%
- Intervention adherence and fidelity (at end of feasibility RCT)
 - o Green, amber, and red ratings will be based on the bespoke fidelity tool; as such, the progression criteria will be developed once the tool has been finalised.
- Retention rates (at 90-days ±7 days post-randomisation)
 - o Green: 60% of participants
 - o Amber: 40-60% of participants

- o Red: <40% of participants
- Proportion transferred and/or released during follow-up (at 42- and 90-days ±7 days postrandomisation)

Outcome measures for the cost-effectiveness feasibility analysis will include:

- Completeness of care plans, case notes, and resource use questionnaires
- Potential cost of ET (based on data from the Personal Social Services Resource Unit)
- Assessment of the feasibility of conducting a Budget Impact Analysis (BIA)
- List of suitable variables for a social Return On Investment (ROI) analysis

Outcome measures for the realist-informed process evaluation will include:

• Refined IPT, logic model, and intervention delivery platform.

Secondary Outcomes

WP2:

The acceptability of the measures in the following table will be assessed. These measures were determined using a literature review (PDG, NIHR 202610):

Outcome	Measurement Tool	Measurement Method	Baseline	42-Days (±7 days)	90-Days (±7 days)
Unmet needs in forensic settings	CANFOR-R	Researcher completes in person with prisoner	~	~	~

The Camberwell Assessments of Needs-Forensic Research (CANFOR-R) is a semi-structured interview schedule assessing need in 25 domains. Each domain has 4 sections, covering the absence or presence of needs, formal and informal help needed and received, overall satisfaction with help, and links between need and offending. The CANFOR-R has been used in previous RCTs in prisons settings (35). It is the only measure that: has adequate evidence for content validity, development, and relevance for our population, and has been designed as a progress measure (51). However, the tools ability to measure change in need has not been fully assessed (51). We will explore its responsivity, including an analysis of domains relevant to this population, such as needs relating to communication, day-time activities, education, physical health, selfcare, and social contact. We will apply the Met Needs Index to CANFOR-R scores for relevant domains (52).

Adult social care outcomes	ASCOT SCT4	Researcher completes in person with prisoner	~	~	>
		prisoner			

The Adult Social Care Outcomes Toolkit (ASCOT) SCT4 is a 32-item self-complete measure of adult social care related quality of life across eight dimensions: accommodation cleanliness and comfort, control over daily life, dignity, food and drink, occupation, personal cleanliness and comfort, personal safety, and social participation and involvement. Each question has

Health Research Authority

four response options relating to four outcome states (ideal, no needs, some needs, high-level needs). Raw scores are then converted into numbers that reflect the relative value of that outcome to the general population. Scores range from -0.17 to 1.00, with higher scores indicating better quality of life. We will use this measure to assess adult social care outcomes. We will also assess its suitability to calculate incremental cost per quality adjusted life year (QALY) for a full economic evaluation. This will include analysing data to estimate parameters (means and standard deviations) and explore responsivity. We will also evaluate the extent to which this measure aligns with changes in the CANFOR-R.

quality of life person with prisoner

EuroQol's EQ-5D 5 level (EQ-5D-5L) is a 5-item self-complete measure of health-related quality of life covering the five domains of anxiety/depression, discomfort/pain, mobility, self-care, and usual activities. Each of these has five response levels: no problems, slight problems, moderate problems, severe problems, unable to/extreme problems. The scale generates a five-digit number representing the health profile, which is then converted into a single index score using a scoring algorithm and a value set. The EQ-5D-5L also includes the EQ visual analogue scale (EQ VAS) in which participants self-rate their health on a line with endpoints labelled 'The best health you can imagine' and 'The worst health you can imagine'. We will use this measure to assess health-related quality of life. We will also assess its suitability to calculate incremental cost per QALY for a full economic evaluation. This will include analysing data to estimate parameters and explore responsivity. Finally, we will evaluate the extent to which this measure aligns with changes in the CANFOR-R.

Capability IC	Researcher completes in person with prisoner	_	~	~
---------------	--	---	----------	---

ICEpop CAPability measure for Adults (ICECAP-A) is a 5-item self-complete questionnaire that assesses five capabilities important to wellbeing, these being feeling settled and secure; love, friendship, and support; being independent; achievement and progress; and enjoyment and pleasure. Each is scored on a scale from 1 (full capability) to 4 (no capability). These individual scores are then converted to a single capability index score between 0 and 1 using a UK population value set. We will use this measure to assess capability. We will also assess its suitability to calculate years of full capability (YFC) for a full economic evaluation. This will include analysing data to estimate parameters and explore responsivity. Finally, we will evaluate the extent to which this measure aligns with changes in the CANFOR-R.

service use prisoner

The Recovering Quality of Life (ReQoL-10) is a 10-item self-report measure assessing quality of life during recovery for people with different mental health conditions. Items have been drawn to cover areas of quality of life that are important for service users, such as activity (meaningful), belonging and relationships, choice, control and autonomy, hope, self-perception, well-being, and physical health. Each item has five response options, which are allocated scores between 0 and 4. The ReQoL-10 is scored by summing scores across questions. Total scores range from 0 to 40, where a higher score indicates a better quality of life. We will use this measure to assess recovery. We will also assess its suitability to calculate incremental cost per QALY for a full economic evaluation. This will include analysing data to estimate parameters and explore responsivity. Finally, we will evaluate the extent to which this measure aligns with changes in the CANFOR-R.

Resource Use Questionnaires Person with prisoner
--

Resource use questionnaires that have previously been developed and tested in community samples (53) will be used to assess receipt of health, personal, and other care services. These will be completed based on care plans, case notes, and discussions with prisoners.

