¹ Made by Mortals is a Community Interest Company managed by and for individuals with lived experience of services and underserved populations including the NHS and/or social care.

² There are three stages in determining eligibility under the Care Act: it must be shown that the person's needs relate to a physical or mental impairment or illness; the person must be unable to achieve at least Empowered Together (Coordinated Social Care in Prison)/ET IRAS ID: 361615 Version 1: 01/08/2025

Health Research Authority

	Realist-informed formative process evaluation:
	·
	 Adult prisoners from the control and intervention arms of the RCT, including those who have withdrawn.
	ET workers (coordinators) involved in assessment and
	 care coordination and their professional supervisors. Healthcare, prison, and local authority staff involved in delivering or supporting the social care of those in the intervention and control groups.
	The other activities in WP2 will be completed by the research team, without participant involvement.
Planned Sample Size	WP1 Activities:
	Training and supervision manual for ET workers (2 workshops):
	12 participants
	Audio, film, and blog development (6-8 workshops):
	8 participants
	WP2 Activities:
	Feasibility RCT:
	 Anticipated N to screen will be between 150 and 250 with a current estimate of 190; with 76 of these then recruited into the feasibility RCT (38 per arm)
	Realist-informed formative process evaluation:
	 An estimated 48 participants will be recruited: 20 prisoners from the control and intervention arms All ET staff: 2 ET workers and 2 supervisors 24 healthcare, prison, and local authority staff
ADDITIONAL INFOR	MATION SPECIFIC TO THE WP2 FEASIBILITY RCT
Treatment Duration	The feasibility RCT will last nine months in total. Recruitment will occur during the first six months to allow the final participants time to complete the three-month intervention.
Follow-Up Duration	The feasibility RCT will include follow-ups at 42-days (six weeks) and 90-days (three months) (±7 days) post-baseline.
Planned Trial Period	The feasibility RCT will last nine months in total.
Outcome Measures	Primary ³ :
	1. Implementation of ET at each site
	2. Recruitment (numbers screened, eligible, and recruited)

two of ten outcome domains of the Care Act (e.g., dressing, toileting); and it must be shown that the inability to achieve these outcomes has a significant impact on the person's wellbeing.

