9. STATISTICS AND DATA ANALYSIS

9.1 Sample Size Calculation

WP1:

The estimated sample size for the workshops for developing the manual for ET workers is N=12, whilst that for the workshops for developing the audio, blog, and film content is N=8. These group sizes will allow for effective communication, diverse perspectives, and meaningful participation.

WP2:

For the feasibility RCT, the target sample size target is N=76 (N=38 per arm). This has been derived from use of a traffic light system to determine whether an RCT is feasible. It is based on the feasibility objectives in relation to the RAG criteria that tests against being in the RED zone (unacceptable outcome) based on an expectation of being in the GREEN zone (acceptable outcome), along with the sample size to give high power to reject being in the RED zone if the GREEN zone holds true (3). The three key feasibility objectives are to assess: (i) recruitment uptake (percent of screened patients recruited), (ii) treatment fidelity, and (iii) participant retention (follow up):

i. Based on the recruitment rate, if we assume the upper boundary of the RED zone is 40% and the lower boundary of the GREEN zone is 60% (designating unacceptable and

- acceptable recruitment respectively), the sample size required for analysis given 80% power and one-sided 5% alpha would be at least N=42 (total screened participants).
- ii. Based on treatment fidelity (defined as having completed the ET assessment and having a written management plan or having been given written resources), if we assume the upper boundary of the RED zone is 60% and the lower boundary of the GREEN zone is 80%, the sample size required for analysis given 80% power and one-sided 5% alpha would be at least N=38 (intervention only).
- iii. Based on follow-up at 90 days, if we assume the upper boundary of the RED zone is 60% and the lower boundary of the GREEN zone is 80%, the sample size required for analysis given 80% power and one-sided 5% alpha would be at least N=38 (total randomised).

The sample sizes across criteria (i)-(iii) are at different levels; (i) is at the level of screened patients, whereas (ii)-(iii) are at the level of recruited patients. To meet criteria (i) we need ns \geq 42 (although we will screen approx. ns \geq 190 (i.e. (1/0.40) × nr (76)) where 0.40 is the expected proportion uptake of the total number screened), and for (ii)-(iii), we need nr = 76 (38 per arm) based on (ii)).

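### The recruitment progression criterion is a conversion percentage that ignores the target of 76 and the six-month window, so it can rate GREEN when accrual has failed

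*Protocol*

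**What the plan says.** Section 2.2 lists the progression criteria for the feasibility RCT. The recruitment criterion is headed "Number screened, eligible, and recruited into trial (once marked eligible from screening" and has three bands: "Green: 60% of participants recruited", "Amber: 40-60% of participants recruited" and "Red: <40% of participants recruited". No band contains a number of people or a time.

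Section 9.1 describes the same objective as "i) recruitment uptake (percent of screened patients recruited" and sizes it on the same cut-points: "if we assume the upper boundary of the RED zone is 40% and the lower boundary of the GREEN zone is 60" per cent. The stated minimum is 42 screened participants, for 80% power at a one-sided 5% level.

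The accrual plan stands elsewhere. The Trial Summary gives a screening range of 150 to 250, "with a current estimate of 190; with 76 of these then recruited into the feasibility RCT (38 per arm". On timing it says "Recruitment will occur during the first six months to allow the final participants time to complete the three-month intervention". Section 9.1 obtains the 190 by dividing 76 by an expected uptake of 0.40 among those screened. The table in section 2.3 says only that this outcome is evaluated at the end of the trial period.

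**The concern.** The heading of the criterion promises numbers, but the bands are a ratio. A ratio says how willing people are to join once they have been found. It does not say whether two prisons can find and randomise enough of them in the time available. Section 2.1 makes the assessment of recruitment rates a primary objective, and none of the other criteria in section 2.2 (delivery, outcome completion, fidelity, retention, transfer or release) compares enrolment with the plan.

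The ratio also starts late. Sections 3 and 6.1 place a separate consent before the ET screen. A person who declines at that step is never ET-screened or marked eligible, and so cannot lower a conversion rate counted from either of those stages.

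At stake is the checkpoint decision. Sections 6.9 and 13.1 say that the programme will progress to a full RCT if minimum success criteria are met. A GREEN for recruitment could sit beside evidence that the pace a full trial needs was not reached.

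**Working it through.** **Inputs.** Bands of 60%, 40-60% and <40% (section 2.2). Null 0.40, alternative 0.60, 80% power, one-sided alpha 0.05, minimum 42 screened (section 9.1). Target 76; screening estimate 190, range 150-250; six-month recruitment period; two prisons (Trial Summary, section 9.1).

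**1. The Protocol's figure of 42.** One-sample test of a proportion by the normal approximation:

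n = [(1.645 × √(0.4 × 0.6) + 0.842 × √(0.6 × 0.4)) / 0.20]² = 37.1.

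With continuity correction: n/4 × [1 + √(1 + 2/(n × 0.20))]² = 41.95, rounded up to 42. The exact binomial agrees: with n = 42 and rejection at 23 or more, alpha is 0.0375 and power 0.803. The 42 is correct, and so is the screening figure, 76/0.40 = 190. The problem is what the criterion measures, not its arithmetic.

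**2. Smallest counts that earn GREEN.** The number needed is 0.60 × n, rounded up.

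| Denominator n | Recruits for GREEN | Conversion | Share of 76 |
|---|---|---|---|
| 10 | 6 | 60.0% | 8% |
| 20 | 12 | 60.0% | 16% |
| 30 | 18 | 60.0% | 24% |
| 42 | 26 | 61.9% | 34% |

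Exactly 60% falls in both GREEN and AMBER as written; I read it as GREEN. If it were AMBER, 13 of 20 (65%, 17% of target) makes the same point. The rows for 10, 20 and 30 apply to the section 2.2 denominator, which has no minimum. The row for 42 also meets the section 9.1 minimum.

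**3. What on-plan delivery scores on the section 9.1 denominator** (recruited over screened).

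| Screened | Recruited | Percentage | Rating |
|---|---|---|---|
| 150 | 76 | 50.7% | AMBER |
| 190 | 76 | 40.0% | bottom of AMBER |
| 250 | 76 | 30.4% | RED |

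GREEN with 190 screened needs 0.60 × 190 = 114 recruits, or 114/76 = 150% of target.

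**4. Accrual implied by the plan.** 76/6 = 12.7 randomisations a month, or 6.3 per prison per month. No band refers to either figure.

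Putting steps 2 and 3 together, on the section 9.1 denominator 26 recruits from 42 screened rate GREEN, while all 76 from 190 screened rate AMBER. The rating does not track achievement of the target.

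**The case against.** **The shortfall would be seen.** Section 2.2 says the outcomes are reviewed as a whole, section 9.2 reports the numbers at each stage, and section 11 provides central monitoring of recruitment rates with monthly and quarterly committee meetings. Section 9.1 also needs 38 intervention participants for fidelity; 26 recruits would give about 13. All of this stands, and it limits the harm. But the monitoring has no threshold. The holistic clause says only that amber or red need not block progression; it provides no way to lower a GREEN.

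**The bands could mean 60% of the target.** Read alone, the GREEN line could mean 60% of 76, or 46 people, which would be a count. The qualifier about people already marked eligible and the definition in section 9.1 both point to conversion. If a count was meant, the wording still has to change.

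**Section 9.1 sets a floor of 42 screened.** This is fair, and on that denominator the cases of 10, 20 or 30 fall below it. The floor is weak, since 26 of 42 is still GREEN.

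**A stronger reading.** A reader might infer that GREEN is the likely rating whenever accrual fails. The documents do not support that, because they give no consent rate among eligible people, and the probability depends on it. With 20 eligible and 55% consenting, the binomial chance of at least 12 recruits is 0.41. The only uptake figure given is 0.40 of those screened; at that rate the chance of GREEN is 0.06 with 20 screened and 0.003 with 42. The point is that the rule allows a GREEN at low accrual, not that it usually produces one.

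**Conclusion.** The point holds as a defect in a stated decision rule. The recruitment criterion can return GREEN at 16% of target (12 of 20) or, at the Protocol's own minimum sample, at 34% of target (26 of 42). On the section 9.1 denominator it grades exact delivery of the plan at the bottom of AMBER. This rests on reading the bands as conversion percentages, which the text favours, and on taking 60% as inclusive. It needs no assumption about consent rates. The figures for on-plan delivery apply only to the recruited-over-screened denominator. A reader might go further and infer that a failed trial would pass unnoticed or progress automatically on a GREEN. The reported counts, the monitoring and the review of all outcomes together do not support that. What is missing is a rule linking the rating to the accrual the plan itself sets out.

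**What to change.** In section 2.2, add a recruitment criterion on the number randomised across both prisons by the end of the six-month recruitment period, as a share of 76. The sponsor should fix the cut-offs before recruitment starts. For illustration only: GREEN at 80% or more (0.80 × 76 = 60.8, so 61 or more), AMBER from 60% to below 80% (0.60 × 76 = 45.6, so 46 to 60), RED below 60% (45 or fewer). Do not rate recruitment GREEN overall unless this count criterion is also GREEN.

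State one denominator for the conversion criterion, eligible or screened, in both section 2.2 and section 9.1. If it is screened, reconcile the 60% GREEN bound with the 0.40 uptake used to plan screening.

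Report monthly randomisations per prison and, where recorded, the number who declined the ET screen.

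The cost is Protocol wording. Randomisation counts by prison will exist in any case, because randomisation is stratified by prison; the Protocol does not say that refusals of the ET screen are logged. The downside is one more criterion that can be missed.
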